11.2.2 SAEs (Including Deaths) and Adverse Events Leading to Study Drug Discontinuation

Deaths and all SAEs will be presented in listing format. In addition, SAEs and AE leading to study drug discontinuation will be summarized by System Organ Class and MedDRA Preferred Term.

11.3 Analysis of Laboratory Data

Listing and descriptive statistics of laboratory values over time, changes from baseline, and extreme abnormal value on treatment will be provided. Baseline is understood as the last available measurement before study drug administration. Extreme abnormal value on treatment is understood as the on treatment laboratory value which is most significantly away from the reference range. Frequency of subjects with transitions relative to reference range and listing of subjects with significant abnormal laboratory values will be presented as well.

11.3.1 Variables and Criteria Defining Abnormality

Clinical laboratory tests performed are listed in [Table 54](#).

Table 54. Clinical Laboratory Tests

Category	Test Name
Hematology	Hematocrit (Hct) Hemoglobin (Hb) Red Blood Cell Count/Erythrocytes White Blood Cells/Leukocytes Platelet Count/Thrombocytes
Diff. Automatic	Neutrophils (relative count) Eosinophils (relative count) Basophils (relative count) Monocytes (relative count) Lymphocytes (relative count)
Enzymes	AST (GOT) ALT (GPT) Alkaline Phosphatase (AP) Creatine Kinase (CK) Gamma-Glutamyl Transferase (GGT/γ-GT)
Electrolytes	Calcium Sodium Potassium Chloride Bicarbonate
Substrates	Glucose BUN (blood urea nitrogen) Creatinine eGFR (estimated by CKD-EPI formula) Bilirubin Total Bilirubin Direct (if total is elevated) Bilirubin Indirect (if total is elevated) Albumin C-Reactive Protein (CRP) (high sensitivity) Cholesterol, total Triglycerides LDL-Cholesterol HDL-Cholesterol
Urinalysis (dipstick)	Urine pH

11.3.2 Statistical Methods

Analysis of Quantitative Laboratory Parameters (Hematology, Chemistry and Urinalysis)

Though the protocol indicates utilizing the Rheumatology Common Toxicity Criteria (RCTC) scale for grading laboratory values, given that the National Cancer Institute Common Toxicity Criteria for Adverse Events (NCI CTCAE) scale includes a more comprehensive list of laboratory values, the lab analyses based on the NCI CTCAE scale will be presented. Changes from Baseline to each scheduled visit and to the final value in continuous laboratory parameters will be summarized with the mean, standard deviation and median.

If there are multiple post-baseline measurements on the same day, average value will be used.

Shift Tables

Shift tables for changes from Baseline according to the normal range will be provided for each hematology, clinical chemistry and urinalysis (pH only) parameter. Shifts from Baseline to the following endpoints will be considered: minimum value, maximum value and final value. Categories of "low or normal" and "high or normal" will be included at Baseline in addition to the categories of "low," "normal," "high" and "missing." If there are multiple post-baseline measurements on the same day, last value will be used.

Potentially Clinically Significant Laboratory Values

Frequencies and percentages of subjects with post Baseline lab values met the following criteria in [Table 65](#) and [Table 76](#) will be summarized.

Table 65. Criteria for Potentially Clinically Important Chemistry Values

Chemistry Variables	Units	Definition of Potentially Clinically Important Current (Version 4) NCI CTCAE Grade 3 or Greater	
		Very Low	Very High
TBL	mcmol/L		> 3.0 × ULN
ALP	U/L		> 5.0 × ULN
SGOT/AST	U/L		> 5.0 × ULN
SGPT/ALT	U/L		> 5.0 × ULN
Albumin	g/L	< 20	
Glucose	mmol/L	< 2.2	> 13.9
Triglycerides	mmol/L		> 5.7
Creatinine	mcmol/L		> 3.0 × ULN
Sodium	mmol/L	< 130	> 155
Potassium	mmol/L	< 3.0	> 6.0
Calcium	mmol/L	< 1.75	> 3.1
CPK	U/L		> 5.0 × ULN
Total Cholesterol	mmol/L		> 10.34
GGT			> 5.0 × ULN

Table 76. Criteria for Potentially Clinically Important Hematology Values

Hematology Variables	Units	Definition of Potentially Clinically Important Current (Version 4) Grade 3 or Greater	
		Very Low	
Hemoglobin	g/dL	< 8.0	
Platelets count	10 ⁹ /L	< 50.0	
WBC count	10 ⁹ /L	< 2.0	
Neutrophils	10 ⁹ /L	< 1.0	
Lymphocytes	10 ⁹ /L	< 0.5	

A separate listing will be provided that presents all of the subjects and values that are NCI CTCAE toxicity grade 3 or above. For each of these subjects, the whole course of the respective parameter will be listed.

If there are multiple measurements on the same day, the worst value will be used.

Liver Function Tests

Additional summaries will be presented for liver function tests including ALT or serum glutamic-pyruvic transaminase (SGPT), AST or serum glutamic-oxaloacetic transaminase (SGOT), alkaline phosphatase, and total bilirubin. Each laboratory value will be categorized as follows:

- $< 1.5 \times \text{ULN}$
- $\geq 1.5 \times \text{ULN} - < 3.0 \times \text{ULN}$
- $\geq 3.0 \times \text{ULN} - < 5.0 \times \text{ULN}$
- $\geq 5.0 \times \text{ULN} - < 10.0 \times \text{ULN}$
- $\geq 10.0 \times \text{ULN} - < 20.0 \times \text{ULN}$
- $\geq 20.0 \times \text{ULN}$

Shift tables of Baseline to the maximum (relative to the normal range, i.e., the largest multiple relative to the upper limit of normal) values, and from Baseline to final value will be presented using these five categories. A listing of potentially clinically significant liver function laboratory values will be provided. The listing will include all subjects who met any of the following four criteria:

- $\text{ALT} \geq 3 \times \text{ULN}$, or
- $\text{AST} \geq 3 \times \text{ULN}$, or
- Alkaline phosphatase $\geq 1.5 \times \text{ULN}$, or
- Total bilirubin $\geq 2 \times \text{ULN}$.

A listing of possible Hy's Law cases, defined as those who meet all of the following conditions will be provided

- $\text{ALT} > 3 \times \text{ULN}$ or $\text{AST} > 3 \times \text{ULN}$
- Associated with an increase in bilirubin $\geq 2 \times \text{ULN}$

- Alkaline phosphatase $< 2 \times \text{ULN}$

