The laboratory tests listed in [Table 2](#) will be performed by the central laboratory service provider at Visits 1, 2, 4, 6, 8, 10, 12, 16, 20, EOT and at Week 188 follow-up visit ("complete" lab). At Visits 3, 5, 7, 9, 11, 13, 14, 15, 17, 18, 19, 21, only WBC, serum CRP and serum albumin will be collected ("targeted" lab). A local laboratory may be used for selected tests in exceptional cases. Subjects should be fasting for at least 8 hours prior to the blood sample being taken at the "complete" visits, except for screening (see [Appendix C](#)).

Instructions regarding sample collection, sample handling/processing and sample shipping are provided in the Laboratory Manual in the ISF. For time points of laboratory sampling, see [Appendix C](#).

Laboratory results (i.e., all safety laboratory and clinical laboratory data relevant for current clinical practice) of the subjects will be available in real time to the respective investigator (via laboratory reports) and to the sponsor (via the central laboratory website) and selected abnormal laboratory alerts will be flagged to the site and sent to sponsor in real time.

A clinically relevant value may be either in or outside the reference range. Clinically relevant abnormal laboratory test results must be confirmed using an unscheduled visit laboratory kit and should be repeated until normalization or stabilization or until an alternative explanation has been found. Laboratory abnormalities are considered to be adverse events only if they result in discontinuation from the study, necessitate therapeutic medical intervention, and/or if the investigator considers them to be adverse events.

Table 2. Laboratory Tests

Category	Test Name
Hematology	Hematocrit (Hct) Hemoglobin (Hb) Red Blood Cell Count/Erythrocytes White Blood Cells/Leukocytes Platelet Count/Thrombocytes
Diff. Automatic	Neutrophils (relative count) Eosinophils (relative count) Basophils (relative count) Monocytes (relative count) Lymphocytes (relative count)
Diff. Manual (if Diff Automatic is abnormal)	Neutrophils, bands (Stabs) Neutrophils, polymorphonuclear (PMN) Eosinophils Basophils Monocytes Lymphocytes
Enzymes	AST(GOT) ALT(GPT) Alkaline Phosphatase (AP) Creatine Kinase (CK) CK-MB, only if CK is elevated Gamma-Glutamyl Transferase (GGT/γ-GT)
Electrolytes	Calcium Sodium Potassium Chloride Bicarbonate

Table 2. Laboratory Tests (Continued)

Category	Test Name

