6.0 Analysis Conventions

Since this is an open-label continuation study, no statistical test will be conducted. Summary statistics will be provided. Data from preceding studies will be integrated with data from this study in the summaries.

Definition of Baseline

For this study, baseline values are defined as the last non-missing values prior to the first dose of study drug in this study. These baseline values will be referred to as "BL" in this document. Unless otherwise specified, this will be the "baseline" for analysis.

Definition of Rx Days (Days Relative to the Date of First Dose of Study Drug)

Rx days are calculated for each time point relative to the date of first dose of this study. They are defined as the number of days between the day of the first dose of risankizumab and the specific time point. Rx days are negative values when the time point of interest is prior to the first risankizumab dose day. Rx days are positive values when the time point of interest is on or after the first risankizumab dose day. The day of the first dose of risankizumab is defined as Rx Day 1, while the day prior to the first risankizumab dose is defined as Rx Day –1 (there is no Rx Day 0).

Definition of Analysis Windows

All time points and corresponding time windows are defined based on Rx Days.

For efficacy analyses, local tolerability, laboratory parameters, and vital sign variables, analysis windows are constructed using the following algorithm:

- Determine the nominal Rx day for each visit (e.g., Week 4 [4 weeks after Baseline visit] equals Rx Day 28).
- In order to include all post baseline data, the first post-baseline interval starts on the first day and the time after the first dose of risankizumab (Rx Day 1).
- Determine the window around a specific nominal Rx day, are presented in the Protocol Appendix C.
- If more than one assessment is included in a time window the assessment closest to the nominal day will be used. If there are two observations equidistant to the nominal day, the one after the nominal day will be used in analyses. If more than one post baseline assessment is included on the same

day, then the worst assessment on that day will be used in analyses, except those specified in Section [11.0](#).

The protocol specified visits and corresponding time windows used in the efficacy analyses, local tolerability, laboratory parameters, and vital sign variables, are presented in the following [Table 1](#) – [Table 32](#).

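### The SAP's general laboratory shift tables apply a last-of-day rule to the minimum and maximum as well as the final value, so a same-day extreme can be dropped before the extreme is taken

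*SAP*

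**What the plan says.** The Shift Tables paragraph of SAP 11.3.2 covers each hematology and chemistry parameter and urine pH. It names three endpoints: "Shifts from Baseline to the following endpoints will be considered: minimum value, maximum value and final value". It closes with a same-day rule that makes no distinction between them: "If there are multiple post-baseline measurements on the same day, last value will be used".

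Other same-day rules and definitions in the SAP bear on this:

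- **Changes from baseline (11.3.2):** "If there are multiple post-baseline measurements on the same day, average value will be used".
- **Potentially clinically significant values (11.3.2):** "If there are multiple measurements on the same day, the worst value will be used".
- **General convention (6.0):** where several post-baseline assessments fall on one "day, then the worst assessment on that day will be used in analyses, except those specified in Section" 11.0.
- **Extreme values (11.3):** "Extreme abnormal value on treatment is understood as the on treatment laboratory value which is most significantly away from the reference range".
- **Liver function tests (11.3.2):** "Shift tables of Baseline to the maximum (relative to the normal range, i.e., the largest multiple relative to the upper limit of normal) values" are planned, and that subsection has no last-value sentence.

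On repeats, Protocol 5.3.1.1 says: "Clinically relevant abnormal laboratory test results must be confirmed using an unscheduled visit laboratory kit". It does not say when the confirmation takes place.

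**The concern.** A shift to the minimum or maximum is meant to show how far a subject's results moved in each direction at any time after baseline, so it should draw on every post-baseline result. A last-of-day rule is a sensible way to define a final value, but it has no connection with an extreme. Applied first, it can remove the very value the table is meant to show.

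At stake is the accuracy of one set of descriptive safety tables. For tests or directions with no potentially-clinically-important criterion, this shift table is the main categorical summary of extremes, so an out-of-range result lost here has no counterpart in the Grade 3 tables. No efficacy endpoint is involved, and the trial plans no hypothesis test.

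**Working it through.** The plan gives no figure on this point, so there is none to reproduce. The check is of the rule itself.

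**1. Does another section override the rule?** No. The worst-value convention in SAP 6.0 yields to Section 11.0, which is where the last-value sentence stands. Nothing in either document limits that sentence to the final-value shift.

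**2. Effect on one day.** Let a subject have an earlier result *a* and a later result *b* on the same day, with *a* ≠ *b*. The rule keeps *b*. If *a* > *b*, that day's maximum is lost; if *a* < *b*, its minimum is lost. Over the whole course, therefore, kept maximum ≤ true maximum and kept minimum ≥ true minimum.

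**3. Worked example (invented values, CRP in multiples of the upper limit of normal).** Day 29: 0.8. Day 57: 1.6, then 0.9. Day 85: 0.7.

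- Last of day: max(0.8, 0.9, 0.7) = 0.9, classed normal.
- All values: max(0.8, 1.6, 0.9, 0.7) = 1.6, classed high.
- The final value is 0.7 either way.

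**4. How often an extreme is lost, given one same-day pair.** Assume *k* post-baseline days, one of which has two results, and all *k* + 1 values exchangeable. The dropped value is the overall maximum with probability 1/(*k* + 1), and likewise the minimum.

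- SAP visit windows for laboratory tests other than WBC, CRP and albumin: 10 post-baseline windows (Week 8 to Week 188), so 1/11 = 9.1%. A simulation with 400,000 replicates gave 9.0% for the maximum and 9.1% for the minimum.
- SAP Table 1 windows, used for WBC, CRP and albumin: 22 post-baseline windows (Week 4 to Week 188), so 1/23 = 4.3%.

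These figures are conditional on a pair existing. They count loss of the extreme, not a change of normal-range category, which is all a shift table shows. Exchangeability also fails if the repeat was prompted by an abnormal result: if that repeat is normal, the abnormal extreme is lost unless another day's retained result is at least as extreme. The documents do not say how often same-day repeats occur, so the number of subjects affected cannot be computed.

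**5. What other outputs still capture.**

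- The Grade 3 or higher summary and listing use the worst same-day value.
- Liver tests have their own shift to the largest multiple of the upper limit of normal, and listings at lower thresholds.
- The chemistry criteria table has no entry for CRP, BUN, chloride, bicarbonate, LDL or HDL. The hematology criteria table has low limits only, so high WBC has none, and eosinophils do not appear.
- Values below Grade 3 fall outside both criteria tables.

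The exposed part is thus milder out-of-range results outside the liver tests, and tests or directions without a criterion.

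**The case against.** The strongest case against is that the situation may hardly occur. No two safety-laboratory draws are scheduled on one day. Protocol 5.1 allows additional visits for re-testing, and 5.3.1.1 ties confirmation to an unscheduled-visit kit. A re-test on another day leaves the abnormal value in the minimum or maximum. This stands. A reader might infer from the confirmation requirement that same-day repeats are common; the documents do not support that.

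Three other stronger readings also fail:

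- **That the error always favours a normal result.** If the later value is the abnormal one, it is kept. If CRP is high at every draw except the earlier one of a same-day pair, dropping that normal value turns the minimum from normal to high, and the table looks worse.
- **That one affected subject distorts an arm by 25%.** With 8 per substudy randomized 1:1, one subject in 4 is 25%, but that is a denominator and not an error rate. Enrolment is at least 8 per substudy, and safety is also summarised across arms and overall.
- **That the SAP contradicts itself by using average, last and worst in different outputs.** Section 6.0 allows Section 11.0 its own rules, and outputs built under different stated rules may differ. One subject could be normal in the shift table and Grade 3 in the other, but only after a large same-day swing, and the Grade 3 value would still be reported.

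Individual results also remain in the laboratory listings, so the data are not lost. None of this makes a last-of-day rule suitable for a minimum or maximum.

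**Conclusion.** The point holds as a minor error of specification. As written, the general shift tables can report a minimum or maximum that is less extreme in its own direction than the observed one, against the SAP's own definition of an extreme value in 11.3. The size is limited to days with more than one result for a test: unscheduled, probably rare, and of unknown frequency.

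The conclusion assumes that same-day selection comes before the minimum or maximum is taken. That is the natural reading, but the SAP does not spell it out, and the ambiguity is itself a reason to clarify. The conclusion covers the general normal-range shift tables only, not the liver shift table or the Grade 3 outputs.

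**What to change.** In the Shift Tables paragraph of SAP 11.3.2, state that shifts to the minimum and maximum use all post-baseline values, including same-day repeats, and that the last same-day value applies only to the shift to the final value. The cost is one SAP sentence and the matching line in the table program. No new data are needed, and the final-value shift is unchanged.

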5.2.2 Exclusion Criteria

A subject will not be eligible for study participation if he/she meets any of the following criteria:

General Exclusion Criteria

1. Previous exposure to risankizumab.
2. Currently enrolled in another investigational study or less than 30 days (from screening) since completing another investigational study (participation in observational studies is permitted),
3. Use of any restricted medication as specified in [Table 1](#) or any drug considered likely to interfere with the safe conduct of the study.
4. Major surgery performed within 12 weeks prior to assignment or planned within 12 months after baseline (e.g., hip replacement, aneurysm removal, stomach ligation).
5. Known chronic or relevant acute infections including HIV, viral hepatitis and/or tuberculosis as defined by either a positive QuantiFERON® TB test or a positive PPD (purified protein derivative) skin test. Subjects with a positive QuantiFERON® TB/PPD test result may participate in the study if further work up (according to local practice/guidelines) establishes conclusively that the subject has no evidence of active tuberculosis.
6. Any documented active or suspected malignancy or history of malignancy within 5 years prior to screening, except appropriately treated basal or squamous cell carcinoma of the skin or in situ carcinoma of uterine cervix.
7. Evidence of a current or previous disease, medical condition (including chronic alcohol or drug abuse) other than psoriasis, surgical procedure (i.e., organ transplant), medical examination finding (including vital signs and ECG), or laboratory value at the Screening Visit outside the reference range that, in the opinion of the investigator, is clinically significant and would make the study

participant unreliable to adhere to the protocol or to complete the trial, compromise the safety of the subject, or compromise the quality of the data.

8. History of allergy/hypersensitivity to a systemically administered biologic agent or its excipients.
9. Female subject who is pregnant, breastfeeding or is considering becoming pregnant during the study or for approximately 16 weeks after the last dose of study drug.
10. Previous enrollment in this trial.

Disease Specific Exclusion Criteria

For Generalized Pustular Psoriasis

11. Subjects with active ongoing inflammatory diseases other than generalized pustular psoriasis that might confound trial evaluations according to investigator's judgment.

For Erythrodermic Psoriasis

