5.2.3.1 Prohibited Therapy

Uses of the following therapies are prohibited from administration in the time periods specified.

Table 1. Restricted Medications

Medication or Class of Medications	Restriction Duration (Through Week 188 Follow-Up Visit)
secukinumab (Cosentyx®), biologics targeting IL-12 except ustekinumab, IL-17 (except ixekizumab and brodalumab), and/or IL-23 directly	26 weeks prior to randomization
ustekinumab (Stelara®), Tumor Necrosis Factor (TNF)- α inhibitors except infliximab, adalimumab and etanercept	12 weeks prior to randomization
granulocyte and monocyte adsorptive apheresis (GMA)	12 weeks prior to randomization
brodalumab, ixekizumab	4 months prior to randomization
infliximab (Remicade®)	8 weeks prior to randomization
adalimumab (Humira®)	2 weeks prior to randomization
etanercept (Enbrel®) live virus vaccinations	6 weeks prior to randomization
Tofacitinib, apremilast	30 days prior to randomization
any investigational device or product (excludes psoriasis products)	30 days prior to randomization
investigational drug for psoriasis (biologics and non-biologics)	12 weeks prior to randomization, or five half-life if longer
other systemic immunomodulating treatments (e.g., methotrexate, cyclosporine A, corticosteroids, ^a cyclophosphamide)	These therapies have to be unchanged for at least 4 weeks prior to randomization, and any change in the dose should be avoided.
other systemic psoriasis treatments (e.g., retinoids, fumarates, any other drug known to possibly benefit psoriasis)	After Week 16, only dose decreasing will be permitted. Cyclosporine A and systemic corticosteroid will be tapered off after confirmation of a clinical improvement in the opinion of the investigator.
phototherapy (e.g., PUVA)	4 weeks prior to assignment
phototherapy (e.g., UVA, UVB)	2 weeks prior to assignment
topical treatment for psoriasis or any other skin condition (e.g., corticosteroids, ^b vitamin D analogues, vitamin A analogues, retinoids, salicylvaseline, salicylic acid, lactic acid, tacrolimus, tar, urea, α -hydroxy acid [fruit acids])	2 weeks prior to randomization

- a. No restriction on corticosteroids with only a topical effect (e.g., inhalative corticosteroids to treat asthma or corticosteroid drops used in the eye or ear).

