Appendix D. Severity Assessment Criteria Score

Severity assessment criteria score (JDA total score) specified by the Japanese Dermatological Association

A	Assessment of skin symptoms: erythema, pustules, Edema (0 – 9)		
B	Systemic symptoms/assessment of test findings: fever, WBC count, serum CRP, serum albumin (0 – 8)		
o Severity:	Mild	Moderate	Severe
(Total score)	(0 – 6)	(7 – 10)	(11 – 17)

A Assessment of skin symptoms (0 – 9)

	Severe	Moderate	Mild	None
Erythema area (total)*	3	2	1	0
Erythema area with pustules **	3	2	1	0
Edema area **	3	2	1	0

* % vs. BSA (severe: $\geq 75\%$, moderate: $\geq 25\%$ and $< 75\%$, mild: $< 25\%$)

** % vs. BSA (severe: $\geq 50\%$, moderate: $\geq 10\%$ and $< 50\%$, mild: $< 10\%$)

B Systemic symptoms/assessment of test findings (0 – 8)

Score	2	1	0
Fever ($^{\circ}\text{C}$)	≥ 38.5	≥ 37 and < 38.5	< 37
WBC count ($/\mu\text{L}$)	$\geq 15,000$	$\geq 10,000$ and $< 15,000$	$< 10,000$
Serum CRP (mg/dL)	≥ 7.0	≥ 0.3 and < 7.0	< 0.3
Serum albumin (g/dL)	< 3.0	≥ 3.0 and < 3.8	≥ 3.8

Overall Improvement Rating Defined According to JDA Total Score

JDA Total Score Change		Other Criteria	
Markedly improved	Decreased by \geq 3 points	or	No or little symptom of generalized pustular psoriasis
Moderately improved	Decreased by 1 or 2 points	or	\geq 30% reduction of erythema area with pustules compared to baseline, without reaching "no or little symptoms of generalized psoriasis" or, Clinically meaningful improvement in at least 2 of the other parameters of the severity assessment criteria (erythema area, oedema area, WBC count, CRP, fever, serum albumin) AND the sum of the changes in individual JDA components is < 3
Slightly improved	0 points (no change)	and	\geq 20% and $<$ 30% reduction of erythema area with pustules compared to baseline, or, Clinically meaningful improvement in at least 1 of the other parameters of the severity assessment criteria (erythema area, oedema area, WBC count, CRP, fever, serum albumin)
Unchanged	0 points (no change)	and	Does not fulfil the other criteria of "slight improvement"
Worsened	Increased by \geq 1 point	-	-

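### The count of potentially clinically important laboratory values ignores baseline, so abnormalities already present before dosing are tabulated together with new ones

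*SAP*

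**What the plan says.** SAP 11.3.2, under potentially clinically significant laboratory values, plans "Frequencies and percentages of subjects with post Baseline lab values met the following criteria" in the chemistry and hematology tables (printed in the text as Tables 65 and 76). The chemistry table is headed "Definition of Potentially Clinically Important Current (Version 4) NCI CTCAE Grade 3 or Greater". The cut-offs are absolute values or multiples of the upper limit of normal. For repeat measurements, "If there are multiple measurements on the same day, the worst value will be used".

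Baseline is defined for laboratory data in SAP 11.3: "Baseline is understood as the last available measurement before study drug administration". It is used for changes from baseline and for shift tables, but not for this count.

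For adverse events, SAP 11.2.1 requires onset after the first dose. Protocol 8.1.6 also admits worsening after the first dose. Both limit the adverse-event tables to what is new or worse.

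On entry, Protocol 5.2.2 item 7 excludes for a "laboratory value at the Screening Visit outside the reference range that, in the opinion of the investigator", is clinically significant and would compromise safety, data quality or adherence. No numeric limit is given. For background systemic immunomodulators, Protocol Table 1 says: "These therapies have to be unchanged for at least 4 weeks prior to randomization".

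For each subject with a Grade 3 or higher value, SAP 11.3.2 also plans a listing: "For each of these subjects, the whole course of the respective parameter will be listed".

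**The concern.** Read literally, the rule puts two kinds of subject into one percentage: those who developed a Grade 3 or higher value after dosing, and those who brought one in and still had it at some later visit, even if it was improving. Only the first kind corresponds to what the adverse-event tables report.

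The design makes the mixture harder to interpret. There is no control group (Protocol 5.6.1), so no comparator shows a background rate. The cells are very small, so one carried-in subject visibly moves a percentage. Safety data are also summarised at the Week 28 and Week 52 interim analyses (SAP 4.4), so the same figure can recur in successive reports.

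**Working it through.** The documents state no figure for this count, so there is none to reproduce. The check reads the rule, tests who could be affected, and sizes the effect.

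**1. Is there a baseline condition?** SAP 11.3 to 11.3.2 contain no requirement of a lower baseline grade, no requirement of worsening, and no separate row for subjects abnormal at baseline. The reading rests on that absence; the SAP does not say outright that baseline is ignored.

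**2. The rule applied to an assumed course.** The albumin criterion is < 20 g/L. Take a baseline of 15 g/L, then 17, 19, 26, 33 and 38 g/L.
- SAP rule: 17 and 19 are below 20, so the subject is counted.
- Rule requiring the criterion and a higher grade than baseline: no later value is worse than 15, so the subject is not in the main count.
- Had every later value been 20 g/L or above, neither rule would count the subject.

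**3. Which parameters can be affected?** Only those in the two tables.
- Hematology criteria are on the low side only (WBC < 2.0, lymphocytes < 0.5 × 10⁹/L, and so on), so a high WBC cannot trigger one.
- CRP is in neither table.
- Albumin is, but its cut-off of 20 g/L lies well below the limit for the top JDA albumin score in Protocol Appendix D (3.0 g/dL × 10 = 30 g/L).
- Glucose, triglycerides, total cholesterol and liver enzymes are also in the chemistry table.

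**4. Cell sizes.** At least 16 subjects, 8 per disease (SAP 4.3), randomized 1:1 within each substudy (Protocol 5.5.3): 8/2 = 4 per dose and disease.

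**5. Effect of one carried-in subject on a parameter's percentage.**
- Dose-by-disease cell: 1/4 = 25 points.
- Disease column or pooled dose column: 1/8 = 12.5 points.
- Overall: 1/16 = 6.25 points.

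**6. Chance that at least one such subject enters.** If a share p of subjects meets a given criterion at baseline, the chance is 1 − (1 − p)ⁿ. The documents give no p; the values below are assumptions.

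| n | p = 1% | p = 5% | p = 10% |
|---|---|---|---|
| 4 | 3.9% | 18.5% | 34.4% |
| 8 | 7.7% | 33.7% | 57.0% |
| 16 | 14.9% | 56.0% | 81.5% |

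For example, with n = 4 and p = 5%: 1 − 0.95⁴ = 0.185. These are upper limits for the chance of a carried-in count, because the subject must also meet the criterion at a later assessment.

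**7. Do other outputs correct the percentage?** The general shift tables use low, normal and high, so they cannot separate a stable Grade 3 value from a milder abnormality that worsened. The liver shift tables use multiples of the upper limit of normal, but cover only ALT, AST, alkaline phosphatase and total bilirubin. The listing identifies each case. None of these changes the tabulated count.

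**The case against.** The strongest reply is that this count is a deliberately simple and conservative screen. It is labelled post-baseline, not treatment-emergent, and no test or formal dose comparison is planned. With about 16 subjects, the whole-course listing shows every carried-in case, and the shift tables and changes from baseline add to it. Item 7 of the exclusion criteria is most likely to catch precisely the values at Grade 3 or above. Counting only worse grades has its own cost: it would drop a Grade 3 value that normalises and then returns, and worsening within the same grade.

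Much of this stands. It limits the point to one of presentation, and the last argument is the reason for the separate row in the fix. It does not show that the tabulated percentage separates new from pre-existing abnormalities.

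Three stronger readings are tempting and not supported:
- **That the disease itself makes qualifying baselines common, because the JDA score includes WBC, CRP and albumin.** High WBC and CRP cannot meet any criterion, and an albumin low enough for the top JDA score need not be below 20 g/L.
- **That background medication produces such values.** The protocol permits the medication but does not link it to these cut-offs.
- **That the table will show a false drug effect or dose difference.** The SAP makes no such claim for the count, and the number of affected subjects may be zero.

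**Conclusion.** The point holds as a minor, inexpensive improvement. As written, the count mixes new Grade 3 or higher values with those that were present before dosing and persisted to at least one later assessment, which is inconsistent with the way adverse events are handled. Each such subject contributes 25 points in a cell of 4, 12.5 in a column of 8 and 6.25 overall, for the parameter concerned. These figures assume enrolment at the planned minimum with equal allocation. How often it will happen is unknown: assuming 0 to 1 such subject per cell, the contribution is 0 to 25 points. No data are lost under the present plan, because the listing shows them.

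**What to change.** In SAP 11.3.2:
1. Make the main count the subjects with a post-baseline value that meets the criterion and is a higher CTCAE grade than baseline, treating a missing baseline as not abnormal.
2. Add a separate row for subjects who met the criterion at baseline and again after baseline without reaching a higher grade. The two rows then add up to the count now planned.
3. For parameters with both a low and a high criterion (glucose, sodium, potassium, calcium), apply the comparison separately in each direction.
4. Keep the whole-course listing of all Grade 3 or higher values unchanged.

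The cost is a few sentences in the SAP and a baseline-grade condition in the program, using data already collected. Two things need care. Recurrence at the baseline grade, or worsening within it, will appear in the separate row and the listing and not in the main count. The SAP tables give only one cut-off per direction, so Grade 4 limits must be taken from CTCAE to recognise worsening beyond a Grade 3 baseline.
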